13.2. Objective Findings

New and worsening signs and symptoms of underlying or emerging disease must be recorded as AEs. Clinically significant abnormal objective findings (eg, clinical laboratory value, ECG value, and physical examination observation) will also be recorded on the Adverse Event page of the CRF from signing of the informed consent onwards. When a clear diagnosis is available that explains the objective findings, this diagnosis will be recorded as the AE, and not the abnormal objective finding (eg, viral hepatitis will be recorded as the AE, not transaminase elevation). If a definite diagnosis is not available, then record the sign (eg, clinically significant elevation of transaminase levels) or symptom (eg, abdominal pain) as the AE.

Clinical laboratory test results will be reviewed by an investigator as they become available. The investigator must determine the clinical significance of all out of range values. Possibly drug-related or clinically relevant abnormal values of uncertain causality must be repeated. Any abnormal values that persist should be followed at the discretion of the investigator. Laboratory reports will be initialed and dated on all pages by a Form FDA 1572-listed investigator.

All on site ECG tracings and ECG over-read reports will be reviewed by an investigator as they become available. The investigator must determine the clinical significance of all abnormal ECG interpretations on the machine read tracing. Possibly drug-related or clinically relevant abnormal ECGs of uncertain causality must be repeated. Any abnormal ECGs that persist should be followed at the discretion of the investigator. ECG tracings will be initialed and dated on all pages by a Form FDA 1572-listed investigator.

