#### **2.1.3. Visit Windows**

While the Time and Events Schedule of the protocol indicates the visit timing and procedures for each visit, the timing of a subject’s actual visit timing may not be exactly as per the protocol indicated target day/visit window (note that the protocol does not indicate required visit windows, but rather provides clear guidance for visit timing). Consequently, for the purpose of analysis, the conventions outlined below will be used to allocate the data collected at each actual visit to a planned protocol visit by defining analysis visit windows.

The reference day is study Day 1. Definition of baseline and endpoint is provided in [Sections 2.1.5 - 2.1.6](#).

If a subject has 2 or more visits (scheduled or unscheduled) in one analysis visit window, the visit closest to the target day will be used as the study visit for that analysis visit window. The other additional visit(s) in the same analysis visit window will not be included in the by-visit

descriptive summary analyses. However, measurements from this/these other additional visit(s) will be included in the subject listings and in the other safety analyses (eg, Potentially Markedly Abnormal Laboratory Values or the worst case analysis) to assure all on-treatment measurements are included. If 2 study visits occur the same number of days from the target day within the same visit window, the later one will be considered as the study visit for that target day.

Although all (scheduled and unscheduled) visits will be allocated to an analysis visit window, only planned protocol visits for each measurement will be included in the by-visit analyses. All tables and figures presenting data by visit will present only those timepoints where the applicable assessment was scheduled to be collected, unless otherwise noted below. Unscheduled and early termination data will be included for definition of endpoint or overall assessments. Data listings will present all data, regardless of visit.

Table 2 summarizes the analysis visit windows for all questionnaires, laboratory, weight, height, waist circumference, vital signs, ECG, cogstate, tanner stage, menstrual cyclicity, and other safety variables assessed at scheduled visits.

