### **2.1.7. Definition of Aggregated Analysis Timepoint**

Unless otherwise specified, aggregated analysis timepoints will be derived for limited safety assessments (eg, the worst case analysis) as below.

- Any visit in open-label treatment period (extension study): defined as any assessment collected in open-label treatment period.
- Any visit in the first 52 week treatment period (extension study): defined as any assessment collected in the first 52-weeks open-label treatment period (ie, data up to Day 365).

Definition of ‘Any visit in DB treatment period (core study)’ (ie, as any assessment collected in DB treatment period) is same as what were defined in the core studies.

Specifically, above 3 aggregated analysis timepoints in extension study will be generated for the following worst-case analysis:

- Potentially Markedly Abnormal Laboratory Values (PMALV) (Section 2.6.5, Table 3.1)
- Potentially Markedly Abnormal Vital Signs (PMAVS) (Section 2.6.7, Table 7)
- OTc prolongation (Section 2.6.6, Table 4)
- ECG abnormality (Section 2.6.6, Table 5).

See [Sections 2.6.3](#) (Treatment-Emergent Occurrences in OL Period) and [2.6.10](#) (C-SSRS), and [2.6.11](#) UKU for further details about the application of ‘Any visit in DB treatment period (core study)’ and ‘Any visit in open-label treatment period (extension study)’.

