The normal reference ranges for laboratory tests will be used to determine whether the laboratory test value is below, within, or above the normal range. Shifts from DB baseline and shifts from OL baseline over time will be produced by analysis group to show the percentage of subjects with laboratory test values below, within, and above the normal range.

Potentially Markedly Abnormal Laboratory Values (PMALV) per conventional unit and the equivalent International System of Units (SI) for selected laboratory parameters can be found in Table 3.1. The criterion of PMALV is satisfied if a value falls into the potentially markedly abnormal range. The number and percentage of subjects with treatment emergent PMALV in the first 52-weeks treatment period and during overall treatment period, and the number and percentage of subjects who meet the threshold in [Table 3.2](#) per conventional unit and the equivalent International System of Units (SI) by study visit will be presented by analysis group and by analysis subgroup as needed.

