**Table 1.1 Criteria for Potentially Markedly Abnormal Laboratory Values for Pediatric and Adolescent Subjects**

Conventional Unit		SI Unit	
Parameter (Unit)	Potentially Markedly Abnormal Range	Parameter (Unit)	Potentially Markedly Abnormal Range
Hematology			
Hemoglobin (g/dL)	Female: $\leq 9.5$ , Male: $\leq 11.5$ Female or Male: $\geq 17.2$	Hemoglobin (g/L)	Female: $\leq 95$ , Male: $\leq 115$ Female or Male: $\geq 172$
Haematocrit (fraction, %)	$\leq 30, \geq 50$	Haematocrit (V/V)	$\leq 0.3, \geq 0.5$
WBC ( $10^3/\mu\text{L}$ )	$\leq 2.8, \geq 16$	WBC ( $10^9/\text{L}$ )	$\leq 2.8, \geq 16$
RBC ( $10^6/\mu\text{L}$ )	$\leq 3.0, \geq 6.0$	RBC ( $10^{12}/\text{L}$ )	$\leq 3.0, \geq 6.0$
Platelet Count ( $10^3/\mu\text{L}$ )	$\leq 100, \geq 500$	Platelet Count ( $10^9/\text{L}$ )	$\leq 100, \geq 500$
Eosinophils (%)	$\geq 10$	Eosinophils (%)	$\geq 10$
Neutrophils (%)	$\leq 15$	Neutrophils (%)	$\leq 15$
Clinical Chemistry			
ALP (U/L)	$\geq 3 \times \text{ULN}$	ALP (U/L)	$\geq 3 \times \text{ULN}$
ALT (U/L)	$\geq 2 \times \text{ULN}$	ALT (U/L)	$\geq 2 \times \text{ULN}$
AST (U/L)	$\geq 2 \times \text{ULN}$	AST (U/L)	$\geq 2 \times \text{ULN}$
Total Bilirubin (mg/dL)	$\geq 2.0$	Total Bilirubin (umol/L)	$\geq 34.2$
Albumin (g/dL)	$< 50\% \text{ LLN}$	Albumin (g/L)	$< 50\% \text{ LLN}$
Creatinine (mg/dL)	$\geq 2.0$	Creatinine (umol/L)	$\geq 176.8$
Creatine Phosphokinase (CPK) (U/L)	$\geq 450$	Creatine Phosphokinase (CPK) (U/L)	$\geq 450$
LDH (U/L)	$\geq 3 \times \text{ULN}$	LDH (U/L)	$\geq 3 \times \text{ULN}$
GGT (U/L)	$\geq 150$	GGT (U/L)	$\geq 150$
Sodium (mEq/L)	$\leq 130, \geq 150$	Sodium (mmol/L)	$\leq 130, \geq 150$
Potassium (mEq/L)	$\leq 3, \geq 5.5$	Potassium (mmol/L)	$\leq 3, \geq 5.5$
Bicarbonate (mEq/L)	$< 18, > 30$	Bicarbonate (mmol/L)	$< 18, > 30$
Calcium (mg/dL)	$< 8.4, > 11.5$	Calcium (mmol/L)	$< 2.1, > 2.875$
Chloride (mEq/L)	$< 90, > 115$	Chloride (mmol/L)	$< 90, > 115$
Blood Urea Nitrogen (mg/dL)	$\geq 30$	Blood Urea Nitrogen (mmol/L)	$\geq 11.25$

Glucose (fasting) (mg/dL) (random) (mg/dL)	$\leq 45, \geq 126$ $\leq 45, > 200$	Glucose (fasting) (mmol/L) (random) (mmol/L)	$\leq 2.4975, \geq 6.993$ $\leq 2.4975, > 11.1$
Prolactin (ng/mL)	$\geq 1 \times \text{ULN}$	Prolactin (mIU/L)	$\geq 1 \times \text{ULN}$
Lipid Panel (Fasting)			
Total Cholesterol (mg/dL)	$\geq 240$	Total Cholesterol (mmol/L)	$\geq 6.216$

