**Table 3.2 Thresholds for Selected Laboratory Parameters**

Conventional Unit		SI Unit	
Parameter (Unit)	Threshold	Parameter (Unit)	Threshold
Prolactin (ng/mL)	$\geq 1 \times \text{ULN}$	Prolactin (mIU/L)	$\geq 1 \times \text{ULN}$
	$\geq 2 \times \text{ULN}$		$\geq 2 \times \text{ULN}$
	$\geq 3 \times \text{ULN}$		$\geq 3 \times \text{ULN}$
	$\geq 5 \times \text{ULN}$		$\geq 5 \times \text{ULN}$
HDL-C (mg/dL)	$\leq 30$	HDL-C (mmol/L)	$\leq 0.777$
	$\leq 40$		$\leq 1.036$
LDL-C (mg/dL)	$\geq 160$	LDL-C (mmol/L)	$\geq 4.144$
	$\geq 200$		$\geq 5.180$
Total Cholesterol (mg/dL)	$\geq 200$	Total Cholesterol (mmol/L)	$\geq 5.180$
	$\geq 240$		$\geq 6.216$

A listing of subject data for those who have experienced at least once PMALV in the open-label study will be generated.

Urine drug screen results will be presented for each parameter at DB baseline, OL baseline, post-OL baseline visit, W52 endpoint, and endpoint. Number and percentage of positive and negative results will be displayed by analysis group.

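### No planned table counts how many subjects ever reached prolactin ≥2, ≥3 or ≥5 x ULN, LDL-C ≥200 mg/dL or HDL-C ≤30 mg/dL, because SAP 2.6.5 counts these cut-offs only by visit

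*SAP*

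**What the plan says.** SAP 2.6.5 sets two reporting rules in one sentence. The first is for Table 3.1, which is captioned 1.1 where it appears in the body: "The number and percentage of subjects with treatment emergent PMALV in the first 52-weeks treatment period and during overall treatment period". The second is for Table 3.2: "the number and percentage of subjects who meet the threshold in" that table, "per conventional unit and the equivalent International System of Units (SI) by study visit will be presented".

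SAP 2.1.7 defines the any-visit timepoints (first 52 weeks, and the whole open-label period) and lists the worst-case analyses that use them. The only laboratory entry is "Potentially Markedly Abnormal Laboratory Values (PMALV) (Section 2.6.5, Table 3.1"). Table 3.2 is not on the list.

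SAP 2.1.3 governs by-visit tables. One value is used per window, the one closest to the target day. Of the rest it says: "The other additional visit(s) in the same analysis visit window will not be included in the by-visit" summaries. It then limits by-visit tables to planned visits and to timepoints where the assessment was scheduled. Unscheduled and early-termination data go to endpoint or overall assessments.

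**The concern.** Table 3.2 exists to grade severity: prolactin at 1, 2, 3 and 5 x ULN, and two levels for each of three lipids. For a safety question, the natural summary of a graded threshold is the proportion of subjects who crossed it at any time on treatment. The plan gives that summary for prolactin only at the lowest grade, so its one period-level figure pools slight and marked elevations. A reader of the study report who asks what proportion of these children ever had prolactin at 3 x ULN would find a by-visit series and no answer. Long-term safety is part of the primary objective, so the gap falls in a result that the study is meant to deliver.

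**Working it through.** **Step 1. Which cut-offs have a period-level count?** Tables 3.1 and 3.2 side by side (lipids in mg/dL):

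| Analyte | In both tables, so also counted over the period | In Table 3.2 only, so counted by visit only |
|---|---|---|
| Prolactin | ≥1 x ULN | ≥2, ≥3, ≥5 x ULN |
| HDL-C | ≤40 | ≤30 |
| LDL-C | ≥160 | ≥200 |
| Total cholesterol | ≥240 | ≥200 |

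Five cut-offs are more extreme than Table 3.1 and lack a period count: three for prolactin, one for LDL-C and one for HDL-C. For total cholesterol the more extreme level already has one; the level without it is the milder.

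**Step 2. Does another planned output fill the gap?** SAP 2.6.5 also plans descriptive statistics by visit and at the endpoints, shifts between below, within and above normal, and listings. None of these counts subjects by multiple of ULN over a period.

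**Step 3. Can by-visit counts be combined?** No, because they do not show whether the same subjects recur. Let p be the proportion over a cut-off at each of k draws, with everyone observed at each. The proportion ever over it lies between p (always the same subjects) and min(1, kp) (never the same subject twice).

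- k = 5: Visits 6E, 10E, 16E, 22E and 29E/ET (Protocol Appendix A, Table 9).
- N = 271 + 125 + 306 = 702 (SAP 1.2.1).
- p is not in the documents; it is assumed, from 0.5% to 5%, with no dropout.

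| p | Ever over the cut-off | Subjects of 702 |
|---|---|---|
| 0.5% | 0.5% to 2.5% | 4 to 18 |
| 1% | 1% to 5% | 7 to 35 |
| 2% | 2% to 10% | 14 to 70 |
| 5% | 5% to 25% | 35 to 176 |

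**Step 4. Which values can by-visit tables miss?** SAP 2.1.3 can be read in two ways: the closest value wins whether scheduled or not, or only planned visits count. Take a hypothetical subject with a normal scheduled Week 28 draw on Day 197 (the target day) and an unscheduled draw on Day 205 at 5 x ULN, both inside the Day 183 to 210 window. The distances are 0 and 8 days, so the high value is left out on either reading.

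Values outside a laboratory window are also left out. Before the Week 104 window opens on Day 715, the laboratory windows (Weeks 12, 28, 52 and 76, SAP Table 2) cover 4 x 28 = 112 of the 713 days from Day 2 to Day 714. The other 601 days (601/713 = 84%) lie outside. An unscheduled or early-termination draw on one of them enters no by-visit row for Table 3.2. It remains in the listings and, for prolactin, in the ≥1 x ULN count. It enters an Endpoint row only if one is produced and the value is the last.

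**The case against.** The strongest reply is that nothing is lost. All laboratory values are listed, and so is every subject with a Table 3.1 abnormality. SAP 2.1.11 says in general that safety data are summarized by visit, at Week 52 Endpoint and at Endpoint, so a final early-termination value may be graded there. Protocol 13.2 has clinically significant laboratory findings recorded as adverse events, and SAP 2.6.4 counts subjects with at least one occurrence of each term. The study is descriptive and tests no hypothesis.

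Most of this stands, and it makes the matter one of reporting. It does not close the gap. A listing is not a count, Endpoint holds the last value and not the worst, and adverse-event counts are not graded by multiple of ULN and depend on the investigator's judgement. SAP 2.1.3 keeps additional values for worst-case analyses so that all on-treatment measurements are used, but SAP 2.1.7 does not send Table 3.2 to such an analysis.

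A reader might also infer more than the documents support:

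- **That every abnormal value is repeated and the repeat displaces it.** Protocol 13.2 says only that "Possibly drug-related or clinically relevant abnormal values of uncertain causality must be repeated", with no time limit. Displacement also needs the first of the two SAP 2.1.3 readings. With a first draw on Day 194 and a repeat on Day 199 (3 and 2 days from target), the repeat is used on that reading. On the other, the scheduled value stays.
- **That all the higher lipid cut-offs lack a period count.** Total cholesterol ≥240 mg/dL has one.
- **That the Table 3.1 prolactin row is mislabelled.** No rule in the documents requires the same multiple of ULN for every analyte, and the category is called only potentially abnormal.

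**Conclusion.** The point holds as a gap in planned reporting. For five graded cut-offs (prolactin ≥2, ≥3 and ≥5 x ULN, LDL-C ≥200 mg/dL, HDL-C ≤30 mg/dL), the plan produces by-visit counts, possibly endpoint rows, and no count of subjects ever affected. That rests on the text of SAP 2.1.3, 2.1.7 and 2.6.5 and needs no numerical assumption.

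The size of the understatement cannot be fixed from the documents. The ranges above assume an equal proportion at five draws and no dropout, and they cover scheduled values only. A reader might multiply a by-visit percentage by the number of draws to estimate the proportion ever affected. The documents do not support that: it requires that no subject exceeds the cut-off twice, and nothing in the plan says how persistent elevations are. With full persistence the two proportions coincide.

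The SAP treats comparable graded criteria more fully. SAP 2.6.6 gives QTc >460, >480 and >500 msec by visit and also as any occurrence in the first 52 weeks and overall. SAP 2.6.4 counts its YMRS levels of 15, 16 and 20 over both periods. No reason is given for treating Table 3.2 differently, and the change is worth making.

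**What to change.** In SAP 2.1.7, add the Table 3.2 thresholds to the list of worst-case analyses. In SAP 2.6.5, keep the by-visit counts and also present the number and percentage of subjects meeting each Table 3.2 threshold at any visit in the first 52 weeks and at any visit in the open-label treatment period. Use all scheduled, unscheduled and early-termination values, as for QTc. Split the prolactin counts by gender, in line with the prolactin summaries already planned in SAP 2.6.5.

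The cost is a few extra table rows and no new data. The reported prolactin and lipid figures may look less favourable. SAP Section 1 describes the second final database lock and the full study report on all subjects as still to come, so the rows can be added there.

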**Table 1.1 Criteria for Potentially Markedly Abnormal Laboratory Values for Pediatric and Adolescent Subjects**

Conventional Unit		SI Unit	
Parameter (Unit)	Potentially Markedly Abnormal Range	Parameter (Unit)	Potentially Markedly Abnormal Range
Hematology			
Hemoglobin (g/dL)	Female: $\leq 9.5$ , Male: $\leq 11.5$ Female or Male: $\geq 17.2$	Hemoglobin (g/L)	Female: $\leq 95$ , Male: $\leq 115$ Female or Male: $\geq 172$
Haematocrit (fraction, %)	$\leq 30, \geq 50$	Haematocrit (V/V)	$\leq 0.3, \geq 0.5$
WBC ( $10^3/\mu\text{L}$ )	$\leq 2.8, \geq 16$	WBC ( $10^9/\text{L}$ )	$\leq 2.8, \geq 16$
RBC ( $10^6/\mu\text{L}$ )	$\leq 3.0, \geq 6.0$	RBC ( $10^{12}/\text{L}$ )	$\leq 3.0, \geq 6.0$
Platelet Count ( $10^3/\mu\text{L}$ )	$\leq 100, \geq 500$	Platelet Count ( $10^9/\text{L}$ )	$\leq 100, \geq 500$
Eosinophils (%)	$\geq 10$	Eosinophils (%)	$\geq 10$
Neutrophils (%)	$\leq 15$	Neutrophils (%)	$\leq 15$
Clinical Chemistry			
ALP (U/L)	$\geq 3 \times \text{ULN}$	ALP (U/L)	$\geq 3 \times \text{ULN}$
ALT (U/L)	$\geq 2 \times \text{ULN}$	ALT (U/L)	$\geq 2 \times \text{ULN}$
AST (U/L)	$\geq 2 \times \text{ULN}$	AST (U/L)	$\geq 2 \times \text{ULN}$
Total Bilirubin (mg/dL)	$\geq 2.0$	Total Bilirubin (umol/L)	$\geq 34.2$
Albumin (g/dL)	$< 50\% \text{ LLN}$	Albumin (g/L)	$< 50\% \text{ LLN}$
Creatinine (mg/dL)	$\geq 2.0$	Creatinine (umol/L)	$\geq 176.8$
Creatine Phosphokinase (CPK) (U/L)	$\geq 450$	Creatine Phosphokinase (CPK) (U/L)	$\geq 450$
LDH (U/L)	$\geq 3 \times \text{ULN}$	LDH (U/L)	$\geq 3 \times \text{ULN}$
GGT (U/L)	$\geq 150$	GGT (U/L)	$\geq 150$
Sodium (mEq/L)	$\leq 130, \geq 150$	Sodium (mmol/L)	$\leq 130, \geq 150$
Potassium (mEq/L)	$\leq 3, \geq 5.5$	Potassium (mmol/L)	$\leq 3, \geq 5.5$
Bicarbonate (mEq/L)	$< 18, > 30$	Bicarbonate (mmol/L)	$< 18, > 30$
Calcium (mg/dL)	$< 8.4, > 11.5$	Calcium (mmol/L)	$< 2.1, > 2.875$
Chloride (mEq/L)	$< 90, > 115$	Chloride (mmol/L)	$< 90, > 115$
Blood Urea Nitrogen (mg/dL)	$\geq 30$	Blood Urea Nitrogen (mmol/L)	$\geq 11.25$

Glucose (fasting) (mg/dL) (random) (mg/dL)	$\leq 45, \geq 126$ $\leq 45, > 200$	Glucose (fasting) (mmol/L) (random) (mmol/L)	$\leq 2.4975, \geq 6.993$ $\leq 2.4975, > 11.1$
Prolactin (ng/mL)	$\geq 1 \times \text{ULN}$	Prolactin (mIU/L)	$\geq 1 \times \text{ULN}$
Lipid Panel (Fasting)			
Total Cholesterol (mg/dL)	$\geq 240$	Total Cholesterol (mmol/L)	$\geq 6.216$
Triglycerides (mg/dL)	Female: $\geq 170$ , Male: $\geq 200$	Triglycerides (mmol/L)	Female: $\geq 1.921$ , Male: $\geq 2.26$
HDL-C (mg/dL)	$\leq 40$	HDL-C (mmol/L)	$\leq 1.036$
LDL-C (mg/dL)	$\geq 160$	LDL-C (mmol/L)	$\geq 4.144$
Urinalysis			
RBC (hpf)	$> 25$	RBC (hpf)	$> 25$
WBC (hpf)	$> 25$	WBC (hpf)	$> 25$

ULN = Upper Limit of the Normal range. LLN = Lower Limit of the Normal range.

**Table 3.2 Thresholds for Selected Laboratory Parameters**

Conventional Unit		SI Unit	
Parameter (Unit)	Threshold	Parameter (Unit)	Threshold
Prolactin (ng/mL)	$\geq 1 \times \text{ULN}$	Prolactin (mIU/L)	$\geq 1 \times \text{ULN}$
	$\geq 2 \times \text{ULN}$		$\geq 2 \times \text{ULN}$
	$\geq 3 \times \text{ULN}$		$\geq 3 \times \text{ULN}$
	$\geq 5 \times \text{ULN}$		$\geq 5 \times \text{ULN}$
HDL-C (mg/dL)	$\leq 30$	HDL-C (mmol/L)	$\leq 0.777$
	$\leq 40$		$\leq 1.036$
LDL-C (mg/dL)	$\geq 160$	LDL-C (mmol/L)	$\geq 4.144$
	$\geq 200$		$\geq 5.180$
Total Cholesterol (mg/dL)	$\geq 200$	Total Cholesterol (mmol/L)	$\geq 5.180$
	$\geq 240$		$\geq 6.216$

A listing of subject data for those who have experienced at least once PMALV in the open-label study will be generated.

Urine drug screen results will be presented for each parameter at DB baseline, OL baseline, post-OL baseline visit, W52 endpoint, and endpoint. Number and percentage of positive and negative results will be displayed by analysis group.

## 2.6.6. ECG Evaluations

As a part of each ECG, heart rate (HR), axis, and the following intervals will be measured: RR, PR, QRS, and QT. Corrected QT intervals (QTcB and QTcF) values are based on the following formula:

- Bazett:  $QT_cB \text{ (msec)} = QT \text{ (msec)} / (RR/1000)^{1/2}$
- Fridericia:  $QT_cF \text{ (msec)} = QT \text{ (msec)} / (RR/1000)^{1/3}$

where RR is reported in milliseconds (msec).

Descriptive statistics (eg, mean, SD, median, range, 95% CI) for observed value at the DB baseline, OL baseline, each post-OL baseline visit, W52 endpoint, and endpoint and changes from DB baseline and OL baseline, respectively will be displayed for continuous variables (ie, HR, QRS, QTcF, etc) by analysis group.

The overall ECG assessment and ECG tracing results (T wave, U wave, ST segment etc.) are conducted by central reading and a determination is made whether the reading is normal (or absent if applicable) or abnormal. Shifts from OL baseline and Shifts from DB baseline over time will be produced by analysis group.

Bazett and Fridericia corrected QTc values will be classified as having QTc prolongation according to Table 4.

**Table 4 QTc Prolongation for Pediatric and Adolescent Subjects**

QTc Prolongation
QTc >460 msec
QTc >480 msec
QTc >500 msec
Increase from OL baseline QTc $\geq$ 30 msec
Increase from DB baseline QTc $\geq$ 30 msec
Increase from OL baseline QTc $\geq$ 60 msec
Increase from DB baseline QTc $\geq$ 60 msec

The number and percentage of subjects having a QTc prolongation using Fridericia correction method for DB baseline, OL baseline, post-OL baseline visit, W52 endpoint, endpoint, and any treatment emergent occurrence in the first 52-weeks treatment period, and during the open-label treatment period (the worst case), will be summarized by analysis group. A listing of ECG data for subjects with at least one prolonged QTc will also be produced.

For other ECG parameters, subjects will be classified as normal or abnormal using the limits specified in Table 5. For abnormal ECG parameter reporting, counts and percentages of subjects will be presented for DB baseline, OL baseline, each post-OL baseline visit, W52 endpoint, endpoint, and any treatment emergent occurrence in the first 52-weeks treatment period, and during the open-label treatment phase by analysis group.

